### **8.2.1. Study definitions**

PFIZER CONFIDENTIAL

### Time to treatment discontinuation

Time to treatment discontinuation, or persistence, is defined as the difference between the start and end-dates for a treatment episode (accordance with the International Society for Pharmacoeconomics and Outcomes Research (ISPOR) Medication Compliance and Persistence Work Group) regardless of reason for discontinuation. The start date for a treatment episode is defined as the date of first dispensed package and the end date is defined as the date of the last dispensed package with the same ATC code, plus the number of days that package, as well as accumulated medicine (see more details below), is intended to cover. This end date is overruled if there is a new filled prescription of another relevant ATC code or death happens before this, then either of these dates represents the end date. If no end of prescribed supply is recorded, data is censored at latest available date in data.

[figure not shown]
Time to treatment discontinuation will be calculated while allowing for patient accumulation of medicine. The number of days covered by the dispensed volume will be determined based on information in the Summary of Product Characteristics (SPC), the volume of dispensed drug, and for sunitinib in first line also by using the prescriber's dosing instruction on the prescription available in the PDR.

For sunitinib, the treatment is provided in 4 + 2 (or 2 + 1) week cycles, where there is a two-week break in treatment after four weeks of continuous drug intake. Hence, the assumed number of days covered by each filled prescription will be adjusted accordingly (i.e. the 14 or 7 days corresponding to the cycle will be added).

When previously supplied dosing instructions cease to be specified, it is assumed that the daily dosage continues in accordance with the previous treatment pattern. Should there be a completeness issue with the variable containing dose information; the recommended average dose per day according to the SPC for each product will be used instead.

[figure not shown]
For axitinib, the treatment is provided in 4 week cycles, without breaks in between. The analysis relies on data on information relating to dispensed pack size and strength;

PFIZER CONFIDENTIAL

Axitinib is available in pack size of 56 tablets, and in strength 1, 3, 5 and 7 mg. Given the dosing recommendations in SPC, a dispensed pack with the strength 1 mg is assumed to last 14 days, whereas the other packs are assumed to last 28 days.

Patients will be allowed to have gaps between filled prescriptions, but once such a gap exceeds 90 days (the “grace period”) they will be defined as non-persistent. As the Swedish pharmacy system allows patients to refill prescriptions when two-thirds of the previous refill has been consumed (e.g. after two months of a three-month prescription) patients may accumulate large amounts of medication. To account for that, patients will be permitted to accumulate medication from overlapping prescriptions and use it to cover future gaps between filled prescriptions. Figure 1 depicts the effect the grace period and accumulation of medication may have on persistence with the help of scenario 1 and 2.

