## 8. RESEARCH METHODS

### 8.1. Study design

To address the research objectives, the study will be carried out as a national retrospective population-based register study based on data from the NBHW.

Based on the study objectives, the primary endpoint in this study is:

- Time to treatment discontinuation in first line sunitinib patients. Time to event measure from index date to discontinuation of treatment, from 01 July 2005 to 31 December 2019 (assessed from index date up to 180 months). This will be investigated using Kaplan-Meier analysis.

[figure not shown]

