**Figure 1. Grace period and accumulation of medication**

Both scenarios in Figure 1 showcase the same subject having filled three prescriptions (A, B and C) of the index treatment. The “grace period” is set to 90 days. In scenario 1, the 2nd prescription (B) is filled before the initial prescription (A) has run out. In scenario 1, the subject is not allowed to accumulate medication and therefore the subject will discontinue and stop being persistent with medication when the supply from prescription B has run out. In scenario 2, accumulation is allowed enabling filled prescription B to close the gap between B and C so that it is equal to or less than 90 days. The subject is now persistent with medication until the supply from filled prescription C runs out. Hence, both the definition of grace period and allowing for accumulation of medication will affect persistence. To investigate the impact of the length of the grace period a sensitivity analysis with a grace period of 60 and 120 days will be carried out.

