**Table 1. Overview of study variables**

Variable	Role	Data source(s)	Operational definition
Total number of sunitinib 1L patients	Outcome	Prescription Register	Number of sunitinib users with at least one filled prescription (in total and per year over time)
Number of sunitinib 1L 4:2 schedule users	Outcome	Prescription Register	Number of sunitinib users that started on a 4:2 schedule and never had a modification in the schedule (total and per year over time)
Number of sunitinib 1L 2:1 schedule users	Outcome	Prescription Register	Number of sunitinib users that started on a 2:1 schedule and never had a modification in the schedule (total and per year over time)
Number of sunitinib 1L patients that was switched from a 4:2 schedule to a 2:1 schedule	Outcome	Prescription Register	Number of sunitinib users that started on a 4:2 schedule and later was switched to a 2:1 schedule, in total and per year over time

PFIZER CONFIDENTIAL

Total number of axitinib second line patients	Outcome	Prescription Register	Number of axitinib 2L users with at least one filled prescription (in total and per year over time)
Gender	Baseline characteristics	Prescription Register	Male/Female (binary)
Age	Baseline characteristics	Prescription Register	Age will be defined as age at the date of first filled prescription of relevant mRCC medication (continuous; years).
Year of treatment initiation	Baseline characteristics	Prescription Register	Defines the year the treatment was initiated.
Region	Baseline characteristics	Prescription Register	County council of the prescribing physician at first prescription date (categorical), see Table 6 in Annex 3
Time to treatment discontinuation	Outcome	Prescription Register	Time from date of first filled prescription to the end of the prescribed supply, or prescription of other ATC code or death if either of these happen before (details in Section 8.2).
Overall survival	Outcome	Cause of Death Register, Prescription Register	Time from date of first filled prescription of the relevant drug to date of death (number of days) where death is defined as all-cause death; If no date of death is recorded, data is censored at latest available date in data.

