### **8.5. Study size**

An estimated 17,000 to 18,000 patients are diagnosed with RCC between 01 January 2000 and 31 December 2019, approximately 1,000 patients per year. Of these patients, an estimated 4,000 to 5,000 are registered with at least one relevant dispensed prescription for mRCC. Approximately 1,000 of these patients are estimated to have received sunitinib as first line treatment during the investigated period. For axitinib, approximately 300 patients are estimated to have received it in second line during the investigated period.

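### Primary endpoint: a last supply ending by 31 December 2019 counts as discontinuation, although no supply ending after 1 October 2019 can show the required gap of more than 90 days

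*Combined protocol and SAP*

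**What the plan says.** Section 8.2.1 (Time to treatment discontinuation) sets the end of an episode as follows: "the end date is defined as the date of the last dispensed package with the same ATC code, plus the number of days that package" and any accumulated medicine are meant to cover. An earlier death or fill of another listed drug overrides that date. The only censoring rule is "If no end of prescribed supply is recorded, data is censored at latest available date in data".

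Table 1 in section 8.3 repeats the definition: "Time from date of first filled prescription to the end of the prescribed supply", or an earlier drug change or death. It states no gap condition itself and refers to section 8.2 for details.

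The grace period comes later in section 8.2.1: "Patients will be allowed to have gaps between filled prescriptions, but once such a gap exceeds 90 days", the patient is non-persistent. The text with Figure 1 describes a last supply this way: "The subject is now persistent with medication until the supply from filled prescription C runs out". It adds that "a sensitivity analysis with a grace period of 60 and 120 days will be carried out".

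Section 8.1 gives the observation window for the primary endpoint as "from 01 July 2005 to 31 December 2019". Section 8.7 adds no rule for gaps still open at the end of the data.

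**The concern.** The two rules disagree for a patient whose supply runs out shortly before the data stop, with no refill, drug change or death by then. The end-of-supply rule records an event. The grace-period rule cannot yet call the patient non-persistent, because up to 90 days without drug is allowed. Some of these patients would have refilled in early 2020, and counting them as stopped biases time to discontinuation downward.

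This is the primary endpoint for sunitinib, and the same rule serves the secondary axitinib endpoint. Two programmers following different sentences would obtain different failure counts and medians in Tables 4 and 5. The unresolved window also lengthens with the grace period, so the 60- and 120-day runs would mix a data-end effect with the effect they are meant to show.

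Long gaps followed by more treatment do occur. Section 4 explains that the grace period was raised from 30 to 90 days because too many patients who changed schedule were being lost.

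**Working it through.** The plan states no event count or last confirmable date, so there is no figure of its own to reproduce.

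**Dates.** Inputs: data end 31 December 2019 (8.1) and grace periods *g* of 60, 90 and 120 days (8.2.1). The gap must exceed *g*, so the last supply end that can be confirmed is 31 December 2019 minus (*g* + 1) days:

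| *g* | Days subtracted | Last confirmable supply end |
|---|---|---|
| 60 | 61 | 31 October 2019 |
| 90 | 91 | 1 October 2019 |
| 120 | 121 | 1 September 2019 |

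Supply ending from 2 October onward has at most 90 observable days. Counting both end days would move each date by one day.

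**Rough size by hand.** Section 8.5 states: "Approximately 1,000 of these patients are estimated to have received sunitinib as first line treatment during the investigated period"; it gives about 300 for axitinib. Starts are assumed uniform over the 14.5-year window.

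- True episode ends in the last 90 days: 1,000 / 14.5 × 90 / 365.25 ≈ 17 for sunitinib, and 300 / 14.5 × 90 / 365.25 ≈ 5 for axitinib.
- On sunitinib at data end, with an assumed mean duration of 0.75 to 1.5 years: 1,000 / 14.5 × 0.75 ≈ 52, up to 1,000 / 14.5 × 1.5 ≈ 103.
- If 10% to 30% of those are between supplies: 52 × 0.10 ≈ 5, up to 103 × 0.30 ≈ 31 false events.
- Unconfirmable sunitinib events in total: 17 + 5 = 22, up to 17 + 31 = 48.

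**Simulation.** All of these inputs are assumed:

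- exponential time to stopping, median 6, 8 or 11 months for sunitinib and 4, 6 or 8 for axitinib;
- fills covering 42 days (sunitinib, 28 plus a 14-day break) or 28 days (axitinib);
- routine refill delay of 0 to 7 days, with 5%, 15% or 30% of refills delayed 10 to 90 days;
- 0% or 50% of stops followed by death or another listed fill, after a mean of 45 days;
- 400,000 fill histories per scenario, scaled to the set sizes and compared with the uncensored truth.

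| Literal rule | Sunitinib, 1,000 | Axitinib, 300 |
|---|---|---|
| Unconfirmable events | 18–43 (1.9–4.7%) | 1.8–4.5% |
| False events | 6–26 (0.6–2.8%) | 0.6–2.7% |
| Kaplan-Meier median too short by | 0.02–0.31 months | 0.04–0.22 months |

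The unconfirmable counts exclude stops confirmed by a later death or other listed fill. Sunitinib persistence at 12 months is 0.2 to 1.0 percentage points too low.

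**Alternative rules, sunitinib.** Censoring only the unconfirmed patients makes the median 0.04 to 0.24 months too long if done at data end, and 0.03 to 0.20 months too long if done at supply end. These patients include true stoppers, so removing their events while keeping their time at risk understates the stopping rate. A common cut-off at 1 October 2019 is within 0.01 months of the true median in both sets.

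Separately coded repeats gave similar ranges for the literal rule and put the cut-off within about 0.02 months for the full sets. In one scenario, censoring unconfirmed patients made the median 0.7 months too long, because medians jump when fills last 42 days.

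**Recent starters, hypothetical only.** For 150 patients all starting in the last three years, the literal rule makes the median 0.1 to 1.6 months too short. The documents do not show that any schedule group has this pattern.

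**The case against.** The strongest reply is that the end-of-supply sentence cannot be read alone. Taken alone, it would run every episode to the last package whatever the gaps, and the grace period would mean nothing. Table 1 defers to section 8.2, and the Figure 1 text does not discuss the end of the data. On a combined reading, a patient not yet beyond 90 days has no established end and is censored at data end. That reading is coherent, and a careful programmer might adopt it. The plan does not state it, however, and it carries the upward bias shown above.

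The second reply is size. For uncensored exponential times the standard error of the median is about *m* / (ln 2 × √*n*). For sunitinib this is 6 / (0.693 × 31.6) = 0.27 to 11 / (0.693 × 31.6) = 0.50 months, a 95% half-width of about 0.5 to 1.0 months. For axitinib, medians of 4 to 8 months with 300 patients give a half-width of about 0.65 to 1.3. The bias lies below these half-widths, and the study is descriptive. This stands for the full sets.

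Third, the simulation omits early refills, which section 8.2.1 allows once two-thirds of a supply is used. Adding 30% to 50% early refills lowered false events by roughly 1% to 30%, so the ranges lean somewhat high.

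Last, a common cut-off discards deaths and drug changes observed in the final three months. That cost is real but small.

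**Conclusion.** The concern holds. As worded, the primary endpoint turns every last supply ending by 31 December 2019 into an event, while the grace-period rule cannot be checked for supply ending after 1 October 2019. Nothing in the plan resolves the conflict. The dates are exact. The size rests on assumed durations, refill delays and uniform starts, and is modest: up to about 3% of events are false in either full set, and the median is at most about 0.3 months too short, which is below sampling error. It would matter more only for a schedule group that started mostly in the last years, and the documents do not give that distribution. The correction is worth making because it concerns the primary endpoint, the bias has a known direction, and different readings give different tables.

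**What to change.** In section 8.2.1, for time to treatment discontinuation, censor all patients administratively at the last date on which the gap can be confirmed: 1 October 2019 for the 90-day base case, 31 October for 60 days and 1 September for 120 days. Use later dispensings only to confirm that no refill followed. State that patients starting after the cut-off do not contribute to this endpoint, and report their number under Tables 4 and 5. If one evaluable set is wanted for all three runs, use 1 September 2019 throughout; otherwise the set differs slightly between runs. Overall survival stays censored at 31 December 2019.

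The cost is two sentences and a few lines of code. At 90 days, about 3 of 174 months of follow-up is lost for this endpoint, including deaths and drug changes after the cut-off. With uniform starts over 5,297 days, late starters are 61 / 5,297 = 1.15%, 91 / 5,297 = 1.72% and 121 / 5,297 = 2.28% of patients. That is about 12, 17 and 23 of 1,000 on sunitinib and 3, 5 and 7 of 300 on axitinib, for 60, 90 and 120 days.

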#### 4. AMENDMENTS AND UPDATES

Amendment number	Date	Protocol section(s) changed	Summary of amendment(s)	Reason
1	April 13, 2021	8.2	Change from 30 days grace period to 90 days in base case, when calculating treatment duration	Too many of the patients with a switch from 4:2 to 2:1 are lost with a 30 day grace period. The rational to move to 90 days is that the likelihood of having a longer gap is higher than that the patients get a treatment in the gap (it also has to be a treatment that we cannot see, we capture all oral treatments, which makes it even more unlikely)
2	April 13, 2021	8.1, 8.2	Time period for data collection modified; end date for data collection is changed to 31 December 2019	Access to data from SoS

PFIZER CONFIDENTIAL

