## **7. RESEARCH QUESTION AND OBJECTIVES**

The present study is an explorative retrospective study investigating treatment patterns and outcomes for sunitinib and axitinib mRCC patients in a nationwide population-based setting in sweden.

In more detail the primary objective is to:

- Investigate time to treatment discontinuation (treatment duration) for first line treatment with sunitinib for different treatment schedules: 4:2 (4 weeks on/2 weeks off) and 2:1 (2 weeks on/1 week off).

The secondary objectives are to:

- Investigate overall survival (OS) for first line treatment with sunitinib, for different treatment schedules, 4:2 (4 weeks on/2 weeks off) and 2:1 (2 weeks on/1 week off).
- For second line treatment with axitinib, investigate time to treatment discontinuation (treatment duration) and OS.

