## **Dosing Schedule**

The different treatment schedules for sunitinib that will be analysed (starting on 4:2, starting on 2:1 and starting on 4:2 and then switching to 2:1) will be defined based on the dosing instruction provided by the prescriber and will be reviewed manually (the variable DOSER in the Swedish Prescribed Drug Register). In the case no instruction is provided at the start of the treatment, a 4:2 dosing scheme (recommended dose in the SPC) will be assumed. When previously supplied dosing instructions cease to be specified, it is assumed that the daily dosage continues in accordance with the previous treatment pattern. A patient is defined as having switched from a 4:2 to a 2:1 schedule if the dosing instruction clearly indicates this. Other sunitinib dosing schedules than the ones described above will not be included in the analysis but will be included in descriptive statistics.

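### As worded, the sunitinib coverage rule adds one break per fill, so equal fills cover seven more days on 4:2 than on 2:1; a smaller gap concerns supply that ends near the data cut

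*Combined protocol and SAP*

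**What the plan says.** The primary objective (Section 7) is time to discontinuation of first-line sunitinib for two schedules: "4:2 (4 weeks on/2 weeks off) and 2:1 (2 weeks on/1 week off"). Section 8.7 compares the schedule cohorts by Kaplan-Meier, log-rank tests and Cox models adjusted for age, gender, year of initiation and region.

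Section 8.2.1 ends an episode at the last dispensing plus the days that the package and any stock in hand should last. A switch to another relevant drug, or death, ends it sooner. Three statements govern the day count:

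- General rule: "The number of days covered by the dispensed volume will be determined" from the SPC, the volume dispensed and, for first-line sunitinib, the prescriber's instruction.
- Break for sunitinib: the number of "days covered by each filled prescription will be adjusted accordingly (i.e. the 14 or 7 days corresponding to the cycle will be added").
- Stock: "patients will be permitted to accumulate medication from overlapping prescriptions and use it to cover future gaps between filled prescriptions".

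For axitinib the section gives days per pack, for example that "a dispensed pack with the strength 1 mg is assumed to last 14 days". It has no such rule for sunitinib. A gap of more than 90 days makes a patient non-persistent, and 60 and 120 days are sensitivity analyses.

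On the data cut, Section 8.2.1 censors only when no end of supply is recorded. Table 1 likewise takes the end of supply as the event. Data end on 31 December 2019.

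**The concern.** The unit in the break sentence is the filled prescription, and the amount added is a constant that differs by schedule. Two schedules with the same ratio of days on to days off would then get different coverage for the same dispensed amount. The outcome would be measured with a different ruler in each cohort.

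Nothing planned would reveal this. The 60- and 120-day analyses vary the permitted gap and leave the coverage alone. The Cox covariates cannot correct a measurement rule that depends on schedule. Because stock is carried forward, days missing from an early-refilled fill are not recovered later.

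At the data cut, the end-of-supply event and the 90-day rule do not fit together. A patient whose supply ran out shortly before the cut may simply not have refilled yet.

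**Working it through.** **Inputs from the plan.** 4:2 is 28 days on and 14 off; 2:1 is 14 on and 7 off (Section 7). Grace period 90 days, with 60 and 120 as sensitivity; stock accumulates (Section 8.2.1). About 1,000 first-line sunitinib patients (Section 8.5). Fill sizes and refill timing are not given and are assumed below.

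**The plan's own figure.** 2 weeks × 7 = 14 and 1 week × 7 = 7, as stated.

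**Calendar days needed per capsule-day.** (28 + 14)/28 = 1.5 and (14 + 7)/14 = 1.5, the same on both schedules.

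**Coverage per fill.** As worded: capsule-days + 14 or + 7. Needed: capsule-days × 1.5.

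| Capsule-days in the fill | 4:2 as worded | 2:1 as worded | Needed on both |
|---|---|---|---|
| 14 | 28 | 21 | 21 |
| 28 | 42 | 35 | 42 |
| 56 | 70 | 63 | 84 |

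For fills of equal size 4:2 always gets 7 days more. Which schedule is wrong depends on size. At 14 capsule-days 4:2 is 7 days too long, at 28 capsule-days 2:1 is 7 too short, and at 56 both are short (by 14 and 21). A fill of 28 on 4:2 and of 14 on 2:1 is exact on each.

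**Effect on the end date, 28 capsule-day fills.** Take n fills at a constant interval of d days. For a 2:1 patient the true end minus the end as worded is:

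- d ≥ 42: 7 days. The grace period absorbs the earlier gaps, and only the last fill is short.
- 35 ≤ d ≤ 42: 7 + (n − 1)(42 − d).
- d ≤ 35: 42n − 35n = 7n.

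With n = 8:

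| d (days) | 2:1 end as worded | 2:1 end needed (= 4:2) | Shortfall |
|---|---|---|---|
| 42 | 294 + 35 = 329 | 336 | 7 |
| 40 | 280 + 35 = 315 | 336 | 21 |
| 35 or 28 | 8 × 35 = 280 | 336 | 56 |

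These results are identical with grace periods of 60, 90 and 120 days. Section 8.2.1 says that refills are allowed once two-thirds of a supply is used, which for a 42-day supply is day 28. Early refills are therefore possible, but a steady 28- or 35-day interval means stock that keeps growing. It is an upper bound.

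I also simulated equal true persistence on both schedules. The assumptions were an exponential drug-stop time with median 270 days, 28 capsule-day fills, refills timed to remaining stock with a mean delay from −14 to +10 days (SD 10 or 20), and 90-day grace. The 2:1 median came out about 8 to 16 days below the 4:2 median, and 4:2 had no error.

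**Scale.** Assume exponential times, no censoring, a 365-day median and a split of 850 to 150. The standard error of a median is (365/ln 2)/√n: 526.6/√150 = 43.0 and 526.6/√850 = 18.1. For the difference, √(43.0² + 18.1²) = 46.6 days.

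**Data cut.** 31 December 2019 − 90 days = 2 October 2019. Supply that ends on or after that date cannot show a gap above 90 days by the cut. For 60 and 120 days the dates are 1 November and 2 September. In simulations with assumed refill patterns, counting these ends as events shifted the full-set median by 0 to −8 days. Of 1,000 patients, 17 to 37 had an event dated in the last 90 days.

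**The case against.** The best reply is that one break per cycle was meant. Coverage is tied to the volume dispensed, the added days are described as belonging to the cycle, and sunitinib has no fixed pack rule because the prescriber's instruction is read by hand. On that reading nothing is wrong. This stands as a plausible intention, but no sentence says it, and two programmers could code the rule differently and both claim to follow the plan.

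It is also fair that the effect is small. With on-time refills it is 7 days, about 0.15 of the 46.6-day standard error above, and the study is described as exploratory and descriptive. It stays a one-sided error between the cohorts, and more patients do not shrink it.

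A reader might infer three stronger things that the documents do not support.

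- That any one-cycle fill penalises 2:1. It does not: one 2:1 cycle is 14 capsule-days, and the wording gives the correct 21 days.
- That Section 4 shows the fault at work, since "Too many of the patients with a switch from 4:2 to 2:1 are lost with a 30 day grace period". Short 2:1 coverage could produce that pattern. So could real treatment gaps, which is the reason the log gives. It justifies a look at the code and proves nothing.
- That long fills make the error large. The plan mentions refilling "after two months of a three-month prescription", but only as a general example, not as sunitinib practice.

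On the data cut, the 90-day rule can be read to mean that such a patient is not yet non-persistent. Section 8.2.1 and Table 1 nevertheless name the end of supply as the event, so the passages need reconciling.

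**Conclusion.** The concern holds as a defect of wording on the primary endpoint, not as proof of a wrong analysis. Applied as written to fills of equal size, the rule favours 4:2 by 7 covered days per fill. How much of this reaches the end date depends on unstated facts: the fill size on each schedule, how early patients refill, and which version is programmed. Under 28 capsule-day fills the loss for a 2:1 patient runs from 7 days (on-time refills) to 7 days per fill (every refill at least 7 days early). It is zero if breaks are counted per cycle, or if each fill is one cycle of its own schedule. It should be settled before the schedule comparison is reported, because no planned analysis would expose it.

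The data-cut point is secondary. It follows from the text but is small in the full set, and the documents do not support calling the Kaplan-Meier results seriously biased by it.

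**What to change.** **Coverage.** Replace the bracketed explanation in Section 8.2.1 with a formula: days covered = daily doses dispensed over all packages in the fill × 1.5, on both schedules, pro rata for part cycles (14, 28 and 56 daily doses give 21, 42 and 84 days). Add that the factor is not applied again where the average daily dose used as fallback already spreads over the break. Then check which version is coded. The factor is the same for both schedules, so coverage no longer depends on the default in Section 8.2.1: "In the case no instruction is provided at the start of the treatment, a 4:2 dosing scheme" is assumed. This changes only how dispensed supply is counted. It costs one sentence and a code check, with no new data.

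**Data cut.** State in Sections 8.1 and 8.2.1 and in Table 1 that unconfirmed ends of supply are not events. End follow-up for time to discontinuation one grace period before the cut (2 October 2019 in the base case), censor there everyone still persistent, and use later dispensings only to confirm gaps. For the comparison of 60, 90 and 120 days, use one common date, 2 September 2019, so that only the grace period varies.

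The cost is 17 to 37 events per 1,000 patients in the simulations above. With uniform starts over the 5,296 days from 1 July 2005 to 31 December 2019, about 2% of patients also leave this analysis (90/5,296 = 1.7%; 120/5,296 = 2.3% at the common date). Overall survival keeps 31 December 2019. If this counts as a major change to the primary endpoint, Section 8.7 requires a protocol amendment.
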